8.3.2. Analyses of Secondary Serum Immunogenicity (IgA and IgG) Endpoints

Descriptive responses (GMC [also known as GMT per protocol], GMFR, seroconversion) of IgA and IgG against WCE, PT, FHA, PRN, and any additional anti-pertussis antibodies identified during assay development will be conducted at each time point and by treatment group.

To test the hypothesis that BPZE1 and BPZE1 + Boostrix can induce significantly greater serum immunity (IgA, IgG) at Day 29 than baseline, separate paired t-tests will be used to compare the natural log-transformed GMC at Day 29 with the natural log-transformed GMC at baseline within each treatment group. The corresponding 95% CIs will be calculated on the natural log scale, then both lower and upper limits will be exponentiated to get the 95% CIs on the original scale.

A non-inferiority hypothesis will be tested to demonstrate BPZE1 + Boostrix induction of serum IgA is non-inferior to Boostrix at Day 29. An ANCOVA model that includes baseline IgA and treatment group as covariates will be used to compare the natural log-transformed GMCs at Day 29 between BPZE1+Boostrix and Boostrix groups. The non-inferiority margin is set at a 2-fold decrease or -0.693 on natural log scale. Non-inferiority will be demonstrated if the lower limit of the 95% CI of group difference on natural log scale is greater than -0.693.

To test the hypotheses that BPZE1 and BPZE1 + Boostrix can induce significantly greater serum immunity (IgA, IgG) at Day 85 and Day 169/EOS than baseline, separate paired t-tests will be used to compare the natural log-transformed GMC at Day 85 and Day 169/EOS with the natural log-transformed GMC at baseline within each treatment group. The corresponding 95% CIs by treatment group and day will be calculated on the natural log scale, then both lower and upper limits will be exponentiated to get the 95% CIs on the original scale.

The non-inferiority hypothesis will be tested to demonstrate: 1) BPZE1 induction of serum IgA and IgG is non-inferior to Boostrix at Day 85 and Day 169/EOS; 2) BPZE1+ Boostrix induction

of serum IgA and IgG is non-inferior to Boostrix at Day 85 and Day 169/EOS. An ANCOVA model that includes baseline IgA or IgG and treatment group as covariates will be used to compare the natural log-transformed GMCs at Day 85 and Day 169/EOS between either BPZE1 or BPZE1+Boostrix and Boostrix groups. The non-inferiority margin is set at a 2-fold decrease or -0.693 on natural log scale. Non-inferiority will be demonstrated if the lower limit of the 95% CI of group difference on natural log scale is greater than -0.693.

Subgroup analysis by age group (6-10 years and 11-17 years, inclusive, and 10 – 17 years [for requested analyses]), time since last aP vaccination prior to study entry (<median time, \geq median time), or other baseline demographics, and by baseline antibody level (by quantile) will be conducted to examine differential responses to induction of serum immunity (IgA, IgG) at Day 29 by treatment group (BPZE1, BPZE1+Boostrix, and Boostrix). In addition to descriptive summaries, a forest plot of the corresponding 95% CIs will be generated for each subgroup.

To compare BPZE1 and BPZE1 + Boostrix induction of measurable functional antibody (subset of subjects) with Boostrix at Day 29, separate two-sample t-tests will be used to compare between treatment group differences in natural log-transformed GMC at Day 29. The corresponding 95% CIs by treatment group will be calculated on the natural log scale, then both lower and upper limits will be exponentiated to get the 95% CIs on the original scale.

Seroconversion rates with 95% CIs for IgA and IgG will be calculated at Days 29 and 85 by treatment group and day. The 95% CI will be calculated by using Agresti-Coull method. The likelihood ratio chi-square test will be used to compare seroconversion rate between treatment groups. Additional combinations of antibody response (WCE, PT, FHA, PRN, and any additional anti-pertussis antibodies) may also be tested.

Seropositive rates with 95% CIs for IgA and IgG based on Ward Criteria will be calculated at Day 29 by treatment group. The 95% CI will be calculated by using Agresti-Coull method. The likelihood ratio chi-square test will be used to compare seroconversion rate between treatment groups. Ward Criteria Seropositive is defined as increase a 2-fold increase over baseline value (or a 4-fold increase over the lower limit of assay detection whenever the baseline value falls below the lower limit of assay detection) against pertussis toxin (PT), or increase a 2-fold increase over baseline value (or a 4-fold increase over the lower limit of assay detection whenever the baseline value falls below the lower limit of assay detection) against 2 other pertussis antigens (pertactin [PRN], filamentous hemagglutinin [FHA], fimbriae serotype 2 and 3 [FIM2/3]).

Graphics of the reverse cumulative distribution curves of anti-pertussis antibody titers for IgA and IgG GMC will be generated for Day 29.

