1.3.2 Known Potential Benefits

The benefits of the study lie primarily in the opportunities to science and humanity. No direct personal benefit from participation in the study can be guaranteed, as the vaccine may or may not confer protection in humans. As Boostrix is an approved vaccine for boosting the immune response to pertussis, tetanus, and diphtheria, a clinical benefit of receiving this vaccine has been established. All subjects will have the benefit of receiving Boostrix either during the study (if randomized to receive Boostrix) or at study conclusion (at the discretion of the investigator).

2 Study Objectives and Endpoints

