2.2.4. Serum Immunogenicity (IgA and IgG)

- To demonstrate that BPZE1 (BPZE1, BPZE1 + Boostrix) induction of serum immunity is significantly greater than baseline at Day 29.
- To demonstrate that BPZE1 + Boostrix induction of serum immunity is non-inferior compared to Boostrix at Day 29 (BPZE1 + Boostrix vs Boostrix).
- To demonstrate that BPZE1 (BPZE1, BPZE1 + Boostrix) induction of serum immunity remains significantly greater than baseline over the course of the study and at Day 169/EOS and to assess antibody decay curves for BPZE1, BPZE1 + Boostrix and Boostrix.
- To demonstrate that BPZE1 induction of serum IgA is non-inferior to Boostrix at Day 169/EOS (BPZE1 vs Boostrix; BPZE1 + Boostrix vs Boostrix)
- To assess if age, time since last aP vaccination (prior to study entry), or other baseline demographics have a differential response to BPZE1 or Boostrix at Day 29 (BPZE1, BPZE1 + Boostrix, Boostrix).
- To assess if baseline antibody values, by baseline quantile, have variable serum immunity responses at Day 29 when BPZE1 is given alone or with Boostrix or Boostrix alone (BPZE1, BPZE1 + Boostrix, Boostrix).
- To demonstrate that BPZE1 (BPZE1, BPZE1 + Boostrix) induces a measurable functional antibody response (subset of subjects) at Day 29; and to assess whether there is similar magnitude as that seen with Boostrix (BPZE1 vs BPZE1 + Boostrix vs Boostrix).
- To assess for seroconversion at Days 29 and 85 (BPZE1, BPZE1 + Boostrix, Boostrix). Additional combinations of antibody response (WCE, PT, FHA, PRN) may also be tested.

- To assess reverse cumulative distribution curves for immune responses (IgA and IgG) at Day 29.

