3.2.2.4. Serum Immunogenicity

WCE, PT, FHA, PRN, and any additional anti-pertussis antibodies identified during assay development using GMT and GMFR unless otherwise stated.

- BPZE1 and BPZE1 + Boostrix induction of serum immunity (IgA, IgG) at Day 29 compared with baseline (tested independently by treatment group).
- BPZE1 + Boostrix induction of serum immunity (IgA, IgG) compared with Boostrix at Day 29.
- BPZE1 and BPZE1 + Boostrix induction of serum immunity (IgA, IgG) at Day 85 and Day 169/EOS compared with baseline (tested independently by treatment group and day).
- Antibody decays (IgA, IgG) over the course of the study (tested independently by treatment group).
- BPZE1 induction of serum IgA compared with Boostrix at Day 169/EOS.
- BPZE1 + Boostrix induction of serum IgA compared with Boostrix at Day 169/EOS.
- BPZE1, BPZE1 + Boostrix, and Boostrix induction of serum immunity (IgA, IgG) by age, time since last aP vaccination (prior to study entry), or other baseline demographics at Day 29 (tested independently by treatment group).
- BPZE1, BPZE1 + Boostrix and Boostrix induction of serum immunity (IgA, IgG) at Day 29 by baseline quantile (tested independently by treatment group).
- BPZE1 and BPZE1 + Boostrix induction of measurable functional antibody (subset of subjects) compared with Boostrix at Day 29 (tested independently by treatment group).
- Seroconversion rate for serum immunity (IgA, IgG) defined as a 2-fold increase over baseline value; or a 4-fold increase over the lower limit of assay detection (whenever the baseline value falls below the lower limit of assay detection) at Days 29 and 85 (tested independently by treatment group and day).
- Reverse cumulative distribution curves of GMT at Day 29 by treatment group.

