Immunogenicity endpoints (seroconversion, GMT/GMC/GMR, and GMFR) will be summarized by baseline PRN negative and PRN positive status, by quantiles of each anti-pertussis antibody (WCE, PT, FHA, PRN, and any additional anti-pertussis antibodies) and by antibody type (eg, S-IgA, IgA, and IgG separately), by the 2 age groups (6 to 10 years and 11 to 17 years, inclusive) and across age groups. An additional age group of 10 to 17 years will be added for some analyses to be able to support a rationale for immunobridging to adults. A forest plot will be generated for subgroups.

The substudy analysis will assess immunogenicity endpoints at baseline and Days 85 and 113 (independently for substudy subjects) and relative to colonization status (colonized/non colonized) at either or both Day 92 and/or 99 following re-vaccination/attenuated challenge at Day 85.

All statistical tests will be 2 sided at 0.05 significance level.

If a substantial number of subjects receive a COVID-19 vaccine that is under an emergency use authorization only, then safety analysis may also assess any AEs that may be confounded by such concomitant vaccine administration during the study.

All data collected will be listed in data listings.

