8.4.3. Analysis of Serum Immunogenicity Endpoints

To test the hypothesis that BPZE1 induction of serum immunity (IgA, IgG) at Day 113 compared with baseline, or Day 113 compared with Day 85, separate paired t-tests will be used to compare the natural log-transformed GMC at Day 113 with the natural log-transformed GMC at either baseline or Day 85 within each treatment group (BPZE1, BPZE1 + Boostrix, Boostrix). The corresponding 95% CIs will be calculated on the natural log scale, then both lower and upper limits will be exponentiated to get the 95% CIs on the original scale.

BPZE1, BPZE1 + Boostrix, and Boostrix induction of serum immunity (IgA, IgG) at Day 113 and Day 169/EOS will be summarized by participation in the substudy (Yes/No) and by treatment group and by timepoint. Separate two sample t-tests will be used to compare the natural log-transformed GMCs at Day 113 and Day 169/EOS between subjects who participated in the substudy and subjects who did not participate in the substudy (Day 169/EOS only), by treatment group and by timepoint.

BPZE1, BPZE1+Boostrix, BPZE1 and BPZE1+Boostrix, Boostrix control induction of serum immunity (IgA, IgG) at Days 29 and 85 will be summarized by protection against colonization (colonized/non-colonized) and by treatment group and by timepoint. Comparison between colonized subjects and non-colonized subjects will be made using separate two-sample t-tests by treatment group and by timepoint.

The number and proportion of subjects with $\geq 50\%$ killing titer (or equivalent) at Day 113 compared to baseline and Day 29 will be summarized by treatment group and by timepoint. The 95% CI will be provided by using Agresti-Coull method. A McNemar test will be used to compare proportions between timepoints in each treatment groups (Day 113 vs baseline; Day 113 vs Day 29).

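### A rise from baseline in the BPZE1 + Boostrix group is taken to show BPZE1 induction of serum immunity, but the within-group test cannot separate BPZE1 from Boostrix

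*SAP*

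**What the plan says.** The serum objective in SAP 2.2.4, repeated in Protocol 2.2, reads "To demonstrate that BPZE1 (BPZE1, BPZE1 + Boostrix) induction of serum immunity is significantly greater than baseline at Day 29". A companion objective extends it to later visits. SAP 8.3.2 turns this into a hypothesis ("To test the hypothesis that BPZE1 and BPZE1 + Boostrix can induce significantly greater serum immunity (IgA, IgG) at Day 29 than baseline") and tests it by paired t-tests that compare log concentration at Day 29 "with the natural log-transformed GMC at baseline within each treatment group". The same is done at Days 85 and 169. Under SAP Section 4, "All statistical tests will be 2 sided at 0.05 significance level".

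Treatment Group B receives both BPZE1 and Boostrix on Day 1; Group C receives Boostrix with nasal placebo (SAP Table 3-1). Protocol 1.3.2 describes the comparator thus: "As Boostrix is an approved vaccine for boosting the immune response to pertussis, tetanus, and diphtheria".

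The planned serum GMC contrasts of BPZE1 + Boostrix with Boostrix are all non-inferiority tests with margin -0.693 on the natural log scale:
- IgG to PT, FHA and PRN at Day 29 (SAP 8.2);
- IgA at Day 29, stated as "BPZE1 + Boostrix induction of serum IgA is non-inferior to Boostrix at Day 29" (SAP 8.3.2);
- IgA and IgG at Days 85 and 169 (SAP 8.3.2).

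For mucosal S-IgA, by contrast, SAP 8.3.1 plans an ANCOVA for the difference between BPZE1 + Boostrix and Boostrix.

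In the substudy, SAP 8.4.3 sets out "To test the hypothesis that BPZE1 induction of serum immunity (IgA, IgG) at Day 113 compared with baseline, or Day 113 compared with Day 85" and applies paired tests in all three groups, two of which had Boostrix on Day 1.

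**The concern.** A paired test in the BPZE1 + Boostrix group estimates one mean: the total change after both vaccines. Nothing in that analysis separates the two contributions. The randomised Boostrix group could supply the missing reference, but this test does not use it. A significant rise is therefore expected whenever Boostrix works, whatever BPZE1 does, yet the objective credits it to BPZE1.

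At stake is interpretation. The combination group's serum results, above all IgG to the three antigens in Boostrix, could be reported as evidence of BPZE1 immunogenicity when they carry little or none. The Day 113 versus baseline comparison in the substudy has the same weakness in the two groups given Boostrix on Day 1, because any remaining Day 1 Boostrix response is still in the difference.

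**Working it through.** **Inputs from the SAP.** Evaluable n = 108 per group (4.1). SD of ln serum IgG: PT 0.8759, FHA 0.8158, PRN 1.4363 (Table 4-2). Planning differences, BPZE1 + Boostrix minus Boostrix: -0.234, -0.019, -0.075 (Table 4-2). Two-sided 0.05, so 2.5% in the upper tail.

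**Assumptions, not in the documents.** The Boostrix-only fold rise F, taken from 1.1 to 2. The baseline to Day 29 correlation r, taken from 0 to 0.7. Equal SD at both visits.

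**Reproducing the plan's figures.** Paired t-test, 107 df, noncentrality 0.35 × √108 = 3.64: power 95.0%, and 0.950² = 90.2% for both groups; the SAP states 95% and 90%. Non-inferiority at 108 per group, noncentrality (difference + 0.693)/(SD × √(2/108)): PT 97.0%, FHA 100.0%, PRN 88.3%; Table 4-2 states 97.0%, 100% and 88.2%. The method matches the plan's.

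**Paired test in BPZE1 + Boostrix when BPZE1 adds nothing.** The true mean ln change is ln F. The SD of the change is SD × √(2(1 − r)), which equals the Table 4-2 SD at r = 0.5. Standardised effect d = ln F/(SD × √(2(1 − r))); noncentrality d × √108. For PRN with F = 2 and r = 0.5, d = 0.693/1.4363 = 0.483 and the rejection probability is 99.9%. With r = 0 the SD is 2.031, d = 0.341, and it is 94.0%.

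| Boostrix-only rise | r | PT | FHA | PRN |
|---|---|---|---|---|
| none | any | 2.5% | 2.5% | 2.5% |
| 1.1-fold | 0.5 | 20% | 22% | 10% |
| 1.25-fold | 0.3 | 60% | 66% | 27% |
| 1.25-fold | 0.5 | 75% | 80% | 36% |
| 1.25-fold | 0.7 | 92% | 95% | 54% |
| 1.5-fold | 0.5 | 99.8% | 99.9% | 83% |
| 2-fold | 0.5 | 100% | 100% | 99.9% |
| 2-fold | 0 | 100% | 100% | 94% |

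At r = 0.5, a Boostrix rise of 1.36-fold (PT), 1.33-fold (FHA) or 1.65-fold (PRN) already gives 95%.

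**With the SAP's own planning differences.** If Boostrix gives 2-fold and the combination differs from it by the Table 4-2 values, the mean change is 0.693 + difference. At r = 0.5 the paired test is significant in 99.97% (PT), about 100% (FHA) and 99.3% (PRN), although no gain over Boostrix is planned for any antigen.

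**Whether the non-inferiority tests expose this.** At a true difference of zero they pass in 99.99% (PT), 99.999% (FHA) and 94% (PRN). They are not designed to detect a missing BPZE1 contribution, and they do not.

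**The difference from Boostrix.** With baseline-adjusted SD = SD × √(1 − r²) = SD × √0.75 at r = 0.5 and 108 per group, the lower 95% limit exceeds 0 in:

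| True BPZE1 + Boostrix minus Boostrix | PT | FHA | PRN |
|---|---|---|---|
| none | 2.5% | 2.5% | 2.5% |
| 1.5-fold increment | 97% | 99% | 66% |
| Table 4-2 planning difference | 0.001% | 1.6% | 0.8% |

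This contrast keeps its nominal error whatever Boostrix does, but it asks about increment, and on the planning values it would almost never be met.

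**The case against.** **Regimen labels.** The hypothesis sentence in SAP 8.3.2 names BPZE1 and BPZE1 + Boostrix as what induces the response, and SAP 3.2.3.2 speaks of induction by Boostrix too, so group names may simply denote regimens. That is a fair reading of those sentences. It does not cover SAP 2.2.4 and Protocol 2.2, where BPZE1 is the subject and the two groups stand in brackets.

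**The added contribution is not wholly untested.** A reader might infer that no analysis compares the combination with Boostrix except for non-inferiority. The documents do not support that. SAP 8.3.2 compares seroconversion at Days 29 and 85 and Ward-criteria seropositivity at Day 29 between groups without a margin, and tests functional antibody against Boostrix; SAP 8.4.3 adds bactericidal titre rises. The planned ANCOVAs will also yield intervals for the GMC difference. These are real partial checks, but none is the stated test of this objective.

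**The BPZE1-alone group.** It receives IM saline and has its own paired test, which an inert BPZE1 passes about 2.5% of the time per comparison. This stands. No rule, however, makes success there a condition for reading the combination result as BPZE1 induction.

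**Difference is not induction.** Requiring BPZE1 + Boostrix to exceed Boostrix asks a different question. BPZE1 could be immunogenic alone and add nothing measurable on top of Boostrix. This also stands and shapes the fix.

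**Conclusion.** The concern holds for the BPZE1 + Boostrix group: a significant rise from baseline there is a regimen effect and cannot demonstrate BPZE1 induction. With a Boostrix-only rise of 2-fold in IgG to PT, FHA or PRN, the test is significant in about 94% to 100% of trials with an inert BPZE1, for correlations from 0 to 0.7. At smaller rises it falls, to 36% for PRN at 1.25-fold and correlation 0.5. These figures rest on an assumed fold rise and correlation and on SDs from the adult study. For serum IgA and for WCE the documents give neither a Boostrix response nor an SD, so the size there is unknown.

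A reader might go further and conclude that the trial would declare an inert BPZE1 immunogenic almost every time. The documents do not support this: the rate depends on the undocumented Boostrix rise, and the valid BPZE1-alone test would usually contradict the claim. Nor is the trial's success at risk. The primary rule (SAP 8.1) concerns mucosal S-IgA, and the key secondary tests (SAP 8.2) are between-group non-inferiority comparisons. The weakness is confined to secondary serum claims and the exploratory Day 113 claims, but it should be corrected before those are reported.

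**What to change.** 1. In SAP 2.2.4 and 8.3.2, rest the conclusion that BPZE1 induces serum immunity above baseline on the BPZE1-alone group only. Report the BPZE1 + Boostrix change from baseline as a response to the regimen.
2. For each antigen and visit, report the baseline-adjusted ANCOVA difference in serum log concentration (BPZE1 + Boostrix minus Boostrix) with its 95% CI, as SAP 8.3.1 already does for S-IgA. Claim an added BPZE1 contribution over Boostrix only if the lower limit exceeds 0. Say plainly that this tests increment, not induction, and that on the Table 4-2 differences it would rarely be met for PT, FHA and PRN.
3. In SAP 8.4.3, for the two groups given Boostrix on Day 1, base any claim about the Day 85 BPZE1 dose on the planned Day 113 versus Day 85 comparison, and label Day 113 versus baseline as a regimen response.

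The cost is SAP wording and some added ANCOVA output; no new samples or visits are needed. The price is that the combination group's baseline tests no longer support a BPZE1-specific claim.

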
Serum immunogenicity (IgA and IgG): WCE, PT, FHA, PRN, and any additional anti-pertussis antibodies identified during assay development using GMT and GMFR unless otherwise stated.
 
NOTE: To also be tested separately in subjects who participate in the optional substudy as exploratory endpoints, to assess response following re-vaccination/attenuated challenge.
	
Secondary objectives	Secondary endpoints

 To demonstrate that BPZE1 (BPZE1, BPZE1 + Boostrix) induction of serum immunity is significantly greater than baseline at Day 29. 	
 BPZE1 and BPZE1 + Boostrix induction of serum immunity (IgA, IgG) at Day 29 compared with baseline (tested independently by treatment group).

 To demonstrate that BPZE1 + Boostrix induction of serum immunity is non-inferior compared to Boostrix at Day 29 (BPZE1 + Boostrix vs Boostrix). 	
 BPZE1 + Boostrix induction of serum immunity (IgA, IgG) compared with Boostrix at Day 29.

 To demonstrate that BPZE1 (BPZE1, BPZE1 + Boostrix) induction of serum immunity remains significantly greater than baseline over the course of the study and at Day 169/EOS and to assess antibody decay curves for BPZE1, BPZE1 + Boostrix and Boostrix. 	
 BPZE1 and BPZE1 + Boostrix induction of serum immunity (IgA, IgG) at Day 85 and Day 169/EOS compared with baseline (tested independently by treatment group and day). Antibody decays (IgA, IgG) over the course of the study (tested independently by treatment group).

 To demonstrate that BPZE1 induction of serum IgA is non-inferior to Boostrix at Day 169/EOS (BPZE1 vs Boostrix; BPZE1 + Boostrix vs Boostrix) 	
 BPZE1 induction of serum IgA compared with Boostrix at Day 169/EOS. BPZE1 + Boostrix induction of serum IgA compared with Boostrix at Day 169/EOS.

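### SAP 8.3.2 does not match the SAP's own serum objectives and endpoints: WCE IgG at Day 29 has no non-inferiority test, and 24 later-day non-inferiority tests match no stated objective or endpoint

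*SAP*

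**What the plan says.** **Objectives and endpoints.** For Day 29, SAP 2.2.4 aims to show that "BPZE1 + Boostrix induction of serum immunity is non-inferior compared to Boostrix at Day 29", and the matching endpoint in SAP 3.2.2.4 names both isotypes: "BPZE1 + Boostrix induction of serum immunity (IgA, IgG) compared with Boostrix at Day 29". For the end of study, the objective is "To demonstrate that BPZE1 induction of serum IgA is non-inferior to Boostrix at Day 169/EOS". Its two endpoints are "BPZE1 induction of serum IgA compared with Boostrix at Day 169/EOS" and "BPZE1 + Boostrix induction of serum IgA compared with Boostrix at Day 169/EOS". Protocol 2.2 states the same objectives and endpoints. SAP 3.2.2.4 names four serum antigens (WCE, PT, FHA, PRN) and leaves room for others found in assay development.

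**Analysis.** For Day 29, SAP 8.3.2 plans only to "demonstrate BPZE1 + Boostrix induction of serum IgA is non-inferior to Boostrix at Day 29". For later days it plans to show that "BPZE1 induction of serum IgA and IgG is non-inferior to Boostrix at Day 85 and Day 169/EOS", and repeats this for BPZE1 + Boostrix. Both use an ANCOVA adjusted for baseline. Non-inferiority is concluded when the lower 95% confidence limit on the natural log scale lies above -0.693. SAP 8.2 applies the same kind of model and the same margin to Day 29 IgG for PT, FHA and PRN, but not WCE.

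**Change control.** SAP section 1 says that the SAP prevails over the protocol where they differ; it gives no rule for two SAP sections that differ. Section 11 declares one change, the added 10 to 17 year age group.

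**The concern.** The two parts of the SAP pull in opposite directions. At Day 29 the analysis is narrower than the endpoint, so one listed comparison falls between 8.2 and 8.3.2. It concerns WCE, the antigen used for the primary mucosal endpoint. At later days the analysis is wider than the endpoint, in isotype (IgG added) and in time (Day 85 added).

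The added tests include BPZE1 alone against Boostrix on IgG. No objective asks for that comparison, and protocol 6.4 itself notes that BPZE1 lacks the purified PT, FHA and PRN content of Boostrix. Each added test carries a margin and a success rule, so a report could state non-inferiority for comparisons that were never endpoints, and its reader could not tell these from the planned ones. Meanwhile a stated Day 29 objective would be answered only in part.

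**Working it through.** **1. The plan's own figure.** The only power stated for serum titre non-inferiority is in SAP 4.1.2, Table 4-2, for Day 29 IgG. Inputs: 108 evaluable per group, one-sided 0.025, margin -0.693, and the tabulated differences d and SDs. The noncentrality is (0.693 + d) / (SD × √(2/108)), with √(2/108) = 0.1361.

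- PT: (0.693 - 0.234) / (0.8759 × 0.1361) = 3.85. Power is 97.0% by the noncentral t; stated 97.0%.
- FHA: (0.693 - 0.019) / (0.8158 × 0.1361) = 6.07. Power is 100%; stated 100%.
- PRN: (0.693 - 0.075) / (1.4363 × 0.1361) = 3.16. Power is 88.2%; stated 88.2%.

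The table reproduces. It covers three of the Day 29 IgG tests and none of the later-day tests.

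**2. Count of comparisons.** Assumption: one test per named antigen (four), as the per-antigen layout of the SAP implies. The documents give no count, and added antigens would raise every figure.

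| Block | Listed (2.2.4, 3.2.2.4) | Analysed in 8.3.2 |
|---|---|---|
| Day 29, BPZE1 + Boostrix vs Boostrix | 2 isotypes × 4 antigens = 8 | 1 isotype × 4 antigens = 4 |
| Later days, each BPZE1 group vs Boostrix | 2 contrasts × 1 isotype × 4 antigens × 1 day = 8 | 2 contrasts × 2 isotypes × 4 antigens × 2 days = 32 |
| Total | 16 | 36 |

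**3. What is missing at Day 29.** Listed 8, less 4 IgA tests in 8.3.2, less 3 IgG tests in 8.2 (PT, FHA, PRN) leaves 1: WCE IgG. Section 8.3.2 still gives it descriptive summaries, a paired t-test against baseline and a between-group chi-square test of seroconversion. None of these is the non-inferiority comparison in the objective.

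**4. What is added later.** 32 - 8 = 24: IgA at Day 85 (2 × 4 = 8), IgG at Day 85 (8) and IgG at Day 169 (8). With 8.2 included, the SAP runs 36 + 3 = 39 such tests, of which 16 - 1 = 15 are listed and 24 are not.

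**5. Scale of error, for illustration only.** If tests were independent and every true difference lay exactly at the margin, the chance of at least one false claim would be 1 - 0.975^8 = 18.3% for 8 tests and 1 - 0.975^32 = 55.5% for 32. Neither condition is realistic: isotypes, antigens and days are correlated and the control arm is shared.

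**The case against.** The strongest reply is that this is a drafting mismatch with little effect.

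- *Day 29 IgG is mostly tested.* PT, FHA and PRN are key secondary endpoints in 8.2, and 8.3.2 avoids repeating them. This stands: a reader might infer that IgG is lost at Day 29, but among the named antigens only WCE is affected.
- *A method for WCE IgG already exists.* The SAP is to be read together with the protocol, and protocol 7.4.3.2 sends all secondary serum endpoints to the general approaches. This stands in part. However, 8.3.2 specifies this very endpoint for IgA alone, and the protocol's general method is a two-sample t-test whereas 8.3.2 uses a baseline-adjusted ANCOVA. The analyst would have to choose.
- *Counting 8 against 32 looks only at the block that grew.* Overall the comparison is 16 listed against 36 in 8.3.2, or 39 with 8.2. This stands, and both counts should be given.
- *A 56% error rate is not a realistic harm.* This stands. If BPZE1 alone gives lower PT, FHA and PRN IgG than Boostrix, differences below the margin would make false claims rarer. For BPZE1 + Boostrix, the Day 29 planning differences lie well inside the margin, and if that persisted a non-inferiority conclusion would be true.
- *Multiplicity is uncontrolled for every secondary test outside the key secondary set, including the 8 listed ones.* This stands, so the point here is the mismatch and not multiplicity in itself.
- *The added tests are prespecified, and all summaries and data will be reported.* This is true, and it weakens any suggestion that unfavourable results would be set aside. It does not supply the missing objective or endpoint.

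**Conclusion.** The mismatch is real and lies inside the SAP, where the precedence rule does not help. Followed as written, the SAP leaves WCE IgG at Day 29 (and IgG for any antigen added later) without the non-inferiority test that its objective calls for. It also applies a non-inferiority success rule to 24 later-day comparisons that have no matching objective or endpoint and no entry in section 11. The counts assume the four named antigens and one test per antigen.

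Three stronger inferences are not supported. WCE IgG is not unanalysed at Day 29; what it lacks is the non-inferiority test. The 18% and 56% figures are not estimates of this trial's error rate. And nothing here touches the primary endpoint or the key secondary conclusions in 8.2. The consequence is confined to the secondary serum objectives: one is answered incompletely, and the planned and unplanned comparisons in the other cannot be told apart.

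**What to change.** In SAP 8.3.2:

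1. Add the Day 29 non-inferiority test of BPZE1 + Boostrix against Boostrix for WCE IgG, and for IgG to any added antigen, with the same baseline-adjusted ANCOVA and the -0.693 margin. Cross-refer PT, FHA and PRN IgG to 8.2.
2. Limit later-day non-inferiority conclusions to IgA at Day 169, for both BPZE1 groups.
3. Report the Day 85 comparisons and the IgG comparisons at Days 85 and 169 as ratios with 95% CIs, labelled exploratory, with no non-inferiority conclusion.

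If the sponsor wants to keep the added comparisons as tests, list them in 3.2.2.4 with an exploratory label and record the change in section 11. Either route makes the endpoint list and the analysis section agree.

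The cost is SAP wording and one more model per affected antigen. No sample, visit or estimate is lost. On the first route the sponsor gives up non-inferiority wording for 24 comparisons that no objective supports.
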